9.4.2. Follow-up process for clarification of information

For critical data points (e.g., EDD, exposure, and outcome data), if there are outstanding questions, discrepancies between forms or missing data, the appropriate HCP will be contacted for clarification. If needed, 3 subsequent attempts will be made at intervals of approximately 2 weeks. If no further information is obtained, qualified registry staff or the principal investigator will make a logical determination on discrepant information based on the available data. All clarifications and/or changes will be documented and traceable.

9.5. Study size

9.5.1. Assessment of study feasibility

To assess the feasibility of this study, data-driven assumptions regarding the prevalence of moderate-to-severe AD, pregnancy, and CIBINQO uptake were made to estimate the number of women who will potentially be exposed to CIBINQO during pregnancy. The prevalence of AD overall among women of childbearing age was assumed to be 5.5%, with 50% having moderate-to-severe AD (Barbarot et al, 2018; Fuxench et al, 2019; Chidwick et al, 2020); the proportion receiving pharmacotherapy was assumed to be 70% (Beck et al, 2014; Boguniewicz et al, 2017; Napolitano et al, 2021). It was further assumed that 3% of those receiving pharmacotherapy would be treated with CIBINQO (Pfizer internal projections). These assumptions were applied to the population of women of childbearing potential in the US (approximately 74.5 million; US Census Bureau, 2020), which yielded an estimated 43,038 women of childbearing potential who will potentially receive CIBINQO each year. After application of the general fertility estimates in the US (56.0 pregnancies per 1,000 women aged 15 to 44 years; Osterman et al, 2022) and the proportion of pharmacotherapy discontinuation during pregnancy among women with moderate-to-severe AD (10% assumed percentage of discontinuation due to severity of symptoms and risk during pregnancy), it was estimated that 6,507 women may potentially be exposed to CIBINQO during pregnancy over the course of 3 years. Given a 3% MCM prevalence among live births (CDC, 2008) in the US general population, these CIBINQO-exposed pregnancies can be expected to result in approximately 195 live births with MCM.

If the registry were to capture one fourth of these births, a total of 49 lives births with MCM may be enrolled.

9.5.2. Sample size

Sample size calculations were performed with SAS® statistical software (version 9.4 or higher, SAS Institute, Cary, NC) and PASS 2021 Power Analysis and Sample Size software (version 21.0.3, CSS, LLC, Kaysville, Utah, USA) for the outcomes of interest. For the calculations, general population prevalence estimates were obtained for most (but not all) of the outcomes of interest from various sources, including the Metropolitan Atlanta Congenital Defects Program (MACDP), the National Vital Statistics System (NVSS), the National Institute for Child Health and Human Development's Consecutive Pregnancies Study and Consortium on Safe Labor Study, and published literature.

The registry will aim to enroll 728 pregnant women, 364 in each cohort. This sample size will afford the study the ability to achieve its primary and secondary objectives. Sample size calculations are based on the primary outcome, MCM, which is also the outcome with the most restrictive denominators and one of the lowest estimates in the general population. For the primary objective (to estimate crude proportions of outcomes), a sample size of 200 participants per cohort will be targeted to estimate the prevalence of MCM with \pm 3% precision; for the secondary objective (to compare proportions of outcomes between cohorts), a sample size of 364 participants per cohort will be targeted to detect a 3-fold increase in the risk of MCM. Regardless of the sample size achieved, the study will be able to fulfill the primary objective and estimate the crude proportion of the study outcomes with varying precision.

For the primary objective, calculations were performed to determine the achievable precision of outcome prevalence estimates for a range of sample sizes. Table 3 presents by outcome the sample size (number of live births or pregnant women, depending on the outcome) required in each cohort to detect a range of precisions, from 1% to 5%. Precision is calculated as the half-width of the two-sided 95% confidence interval using the Wilson (score) method for binomial proportions, and the prevalence of the outcomes of interest observed in the registry was assumed to be equivalent to that of the general population. As shown in Table 3, 145 live births in the analysis population of each cohort are needed to estimate the prevalence of MCM with $\pm 3\%$ precision.

To estimate the number of pregnant women who will need to be enrolled to result in 145 live births, several factors were considered, including the expected proportion of live births in the registry, the proportion of enrolled women expected to be exposed to CIBINQO in the first trimester, and the proportion of enrolled women expected to be excluded from the analysis population. It was assumed that 90% of enrolled women would be exposed in the first trimester, 90% of enrolled pregnancies would result in a live birth (Covington et al, 2010; Veley et al, 2020), and 10% of enrolled women would be excluded from the analysis population due to not having a diagnosis of moderate-to-severe AD, occurrence of pregnancy outcome prior to enrollment (retrospectively enrolled participants), exposure to a known teratogen or an investigational medication during pregnancy outcome data (participants lost to follow-up). Given these assumptions, to attain 145 live births per cohort, 200 pregnant women would need to be enrolled in each of the 2 cohorts of the study population, and a minimum of 400 women would need to be enrolled in the registry. This sample size will

PFIZER CONFIDENTIAL Page 35 of 67 afford the study the ability to estimate the prevalence of MCM in each cohort with $\pm 3\%$ precision with 95% confidence interval.

Outcome	Reference Prevalence	Reference	Denominator	Sample Size Needed per Cohort to Estimate Prevalence with Specified Precision								
				1%	1.5%	2%	2.5%	3%	3.5%	4%	4.5%	5%
МСМ	3.0%	CDC, 2008	Live births	1,143	521	303	201	145	111	89	73	61
SAB	11.8%	Wu et al, 2019	Pregnant women	4,000	1,779	1,002	642	446	328	252	199	162
Stillbirth	0.596%	MacDorman & Gregory, 2015	Live births and stillbirths	333	184	124	93	74	61	52	45	39
Elective termination	18.6%	Jatlaoui et al, 2019	Live births	5,815	2,584	1,453	930	645	474	363	286	232
Preterm birth	8.47%	Martin et al, 2021	Singleton live births	2,983	1,329	750	482	336	248	191	152	124
SGA	10.0%	By definition	Singleton live births	3,461	1,540	868	557	388	286	219	174	141
Postnatal growth deficiency	10.0%	By definition	Singleton live births	3,461	1,540	868	557	388	286	219	174	141

Table 3. Sample Size Calculations for the Primary Objective

CDC = Centers for Disease Control; MCM = major congenital malformation; reference prevalence = prevalence of outcome in general population for pregnant women of any age; SAB = spontaneous abortion; SGA = small for gestational age.

The outcome infant developmental delay is not listed in the table because a published reference rate is not a vailable.

Sample size calculations were performed in the PASS software for the outcomes of interest; precision is calculated as the half-width of the two-sided 95% confidence interval using the Wilson (score) method for binomial proportions.

For the secondary objective, calculations were performed to determine the achievable detectable relative risk for each outcome and a range of sample sizes. Table 4 presents by outcome the sample size (number of live births or pregnant women, depending on the outcome) required in each cohort to detect a range of RR, from 1.5 to 5.5. Sample size calculations were performed using the Fisher's exact conditional test with Walters normal approximation method, and assuming a power of 80%, a 2-sided α level of 0.05, an equal number of women in each cohort (although other sampling ratios were considered), and observed prevalence of the outcomes of interest in the unexposed cohort equivalent to reference comparator prevalence in the general population. As shown in Table 4, 265 live births in the analysis population of each cohort are needed to detect a 3-fold increase in the prevalence of MCM between cohorts, or a relative risk of 3.

Applying the same assumptions previously mentioned, to attain 265 live births per cohort, 364 pregnant women would need to be enrolled in each of the 2 cohorts of the study population, and a minimum of 728 women would need to be enrolled in the registry. This sample size will afford the study the ability to detect a 3-fold increase in the risk of the primary outcome, MCM, for the secondary analysis. Additionally, Table 5 shows that without any adjustments for multiple comparisons, this sample size will offer the study >80% power to detect a 3-fold increase in all other outcomes except stillbirth (for which the study will have 21.4% power to detect a 3-fold increase).

Outcome	Reference Prevalence	Reference Denominator	Denominator	Sampling Ratio	Sample Size Needed per Cohort to Detect Specific RR (Exposed: Unexposed)								
ez	in Non- exposed Group		(Exposed: Unexposed)	RR= 1.5	RR= 2.0	RR= 2.5	RR= 3.0	RR= 3.5	RR= 4.0	RR= 4.5	RR= 5.0	RR= 5.5	
МСМ	3.0%	CDC, 2008	Live births	1:1	2,627	796	413	265	190	146	117	97	82
SAB	11.8%	Wu et al, 2019	Pregnant women	1:1	596	177	90	57	40	30	24	19	16
Stillbirth	0.596%	MacDorm an & Gregory, 2015	Live births and stillbirths	1:1	13610	4142	2159	1389	999	769	619	516	440
Elective termination	18.6%	Jatlaoui et al, 2019	Live births	1:1	343	100	50	31	21	15	12	9	NA ¹
Preterm birth	8.47%	Martin et al, 2021	Singleton live births	1:1	868	260	134	85	60	46	36	30	25
SGA	10.0%	By definition	Singleton live births	1:1	721	215	110	70	49	37	29	24	20
Postnatal growth deficiency	10.0%	By definition	Singleton live births	1:1	721	215	110	70	49	37	29	24	20

Table 4.	Sample Size Calculations for the Secondary Objective
----------	------------------------------------------------------

CDC = Centers for Disease Control; MCM = major congenital malformation; NA = not a vailable; reference prevalence = prevalence of outcome in general population for pregnant women of any age; RR = relative risk; SAB = spontaneous a bortion; SGA = small for gestational age.

The outcome infant developmental delay is not listed in the table because a published reference rate is not available.

Sample size calculations were performed in SAS (version 9.4) for the outcomes of interest using Fisher's exact conditional test with Walters normal approximation method, and assuming a power of 80% and a 2-sided α level of 0.05.

1 For elective termination, a relative risk of 5.5 with a reference prevalence of 18.6% in the unexposed cohort would result in an estimate above 100% in the exposed cohort.

Outcomes	Power Estimate
МСМ	80%
SAB	>80%
Stillbirth	21.4%
Elective termination	>80%
Preterm birth	>80%
SGA	>80%
Postnatal growth deficiency	>80%

Table 5.Power Calculations

MCM = major congenital malformation; SAB = spontaneous abortion; SGA = small for gestational age.The outcome infant developmental delay is not listed in the table because a published reference rate is not available.

Power calculations were performed in SAS (version 9.4) for the outcomes of interest using Fisher's exact conditional test with Walters normal approximation method, and assuming a sample size of 265 per c ohort, a relative risk of 3.0 and a 2-sided α level of 0.05.

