9.7.2. Primary analysis: Crude outcome proportions

Demographic and baseline characteristics will be summarized with descriptive statistics for each cohort. For each continuous variable, the number of observations, median, mean, standard deviation, minimum, and maximum for each cohort will be reported. For each categorical variable, the frequency and percentage in each category by cohort will be reported.

PFIZER CONFIDENTIAL Page 41 of 67 For each exposure group, the proportion of participants with the outcomes of interest will be calculated. The proportion with the outcomes of interest will be calculated as described in Table 6.

In the analysis of MCMs, participants will be classified into exposure groups (CIBINQO exposed or comparator group) based on exposure during the first trimester (i.e., the etiologically relevant window). For all other outcomes, exposure groups will be defined based on exposure at any point during pregnancy. The exposed group will consist of women exposed to CIBINQO during pregnancy. The unexposed comparator group (i.e., primary comparator group) will consist of women not exposed to CIBINQO during pregnancy.

Outcome	Numerator	Denominator				
Primary Outcome – Major Congenital Malformation (MCM)						
Primary analysis: among live births	Live births with confirmed (i.e., adjudicated) MCMs (excluding MCMs not associated with medication exposure) among women with pregnancy outcome data and, based on exposure classifications mea sured during the first trimester	Live births among women with pregnancy outcome data and, if applicable based on cohort, exposure during 1 st trimester				
Sensitivity analysis: among all pregnancy outcomes	Live births and fetal losses with confirmed MCMs (excluding MCMs not associated with medication exposure) a mong women with pregnancy outcome data and, if applicable based on cohort, exposure during first trimester	Live births and fetal losses among women with pregnancy outcome data and, if applicable based on cohort, exposure during 1 st trimester				
Secondary Outcomes						
Minor congenital malformations	Live births with minor congenital malformations among women with pregnancy outcome data	Live births among women with pregnancy outcome data				

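### Section 9.5.2 deducts a CIBINQO-exposure loss from the unexposed comparator cohort, overstating its enrolment minimums by about 11%; separately, Table 5's stillbirth power does not follow from its stated n

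*Protocol*

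**What the plan says.** All of this is in Protocol section 9.5.2 unless stated otherwise.

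- **Live births required.** For the primary objective "145 live births in the analysis population of each cohort are needed" for ±3% precision on MCM. For the secondary objective "265 live births in the analysis population of each cohort are needed to detect a 3-fold increase" in MCM.
- **Conversion to enrolment.** Three losses are assumed: "It was assumed that 90% of enrolled women would be exposed in the first trimester"; "90% of enrolled pregnancies would result in a live birth"; and "10% of enrolled women would be excluded from the analysis population". The text introducing them makes clear that the first refers to exposure to CIBINQO.
- **Targets.** "200 pregnant women would need to be enrolled in each of the 2 cohorts of the study population" (400 in total). With the same assumptions carried over, "364 pregnant women would need to be enrolled in each of the 2 cohorts of the study population" (728 in total).
- **Denominators.** In section 9.7.2 the comparator group consists of women not exposed to CIBINQO in pregnancy. Table 6 gives the MCM denominator as "Live births among women with pregnancy outcome data and, if applicable based on cohort", exposure in the first trimester. For every other outcome, exposure is counted at any point in pregnancy.
- **Table 5.** The footnote assumes 265 per cohort and a relative risk of 3 for all outcomes, using Fisher's exact conditional test with the Walters approximation. Stillbirth power is given as 21.4%, MCM as 80%, and every other listed outcome as above 80%.

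**The concern.** A loss for lack of first-trimester CIBINQO exposure can occur only in a cohort defined by CIBINQO exposure. No comparator leaves the MCM denominator for that reason, and Table 6 recognises this by making the condition depend on cohort. Yet 9.5.2 gives one enrolment figure for both cohorts and presents it as the number needed to reach the live-birth count. If the exposure factor is in that figure, the comparator minimum and both registry totals are wrong as derived quantities.

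The same factor lies behind the 265 in the Table 5 footnote. That is the MCM count after first-trimester attrition, which does not apply to outcomes that count exposure at any time. It is therefore worth checking whether the Table 5 entries follow from 265 and whether any conclusion depends on it.

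**Working it through.** **1. Reproduce the stated enrolment targets.** Inputs from 9.5.2: 145 and 265 live births; retention factors 0.9 (first-trimester exposure), 0.9 (live birth) and 0.9 (not excluded).

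| Divisor | 145 live births | 265 live births |
|---|---|---|
| 0.9 × 0.9 × 0.9 = 0.729 | 198.9 (stated 200) | 363.5 (stated 364) |
| 0.9 × 0.9 = 0.81 | 179.01 | 327.2 |

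Only the three-factor divisor gives 200 and 364, so the exposure factor was used for both cohorts.

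**2. Remove it for comparators.** Rounding up gives 180 and 328. Ratios: 200/180 = 1.11 and 364/328 = 1.11. With the exposed cohort unchanged, totals are 200 + 180 = 380 and 364 + 328 = 692, which is 20 and 36 women fewer.

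**3. What the stated targets yield in the comparator cohort.** 200 × 0.81 = 162 and 364 × 0.81 = 295 live births, against 145 and 265 needed.

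- *Precision.* Wilson half-width at 3% = z/(1 + z²/n) × √(p(1−p)/n + z²/(4n²)). This is 2.997% at n = 145, matching the protocol's 3%, and 2.8% at n = 162.
- *Power.* Walters approximation: Φ{√(4n₁n₂/(n₁+n₂)) × [arcsin√(p₂ − 1/(2n₂)) − arcsin√(p₁ + 1/(2n₁))] − 1.96}. At 80% power and a relative risk of 3 it reproduces the Table 4 sizes exactly: 265 (MCM), 57, 1389, 31, 85 and 70.
  - MCM, 3% against 9%, 265 per cohort: 80.1%.
  - MCM, 295 comparators and 265 exposed: 82.4%.

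**4. Table 5, stillbirth (0.596% against 1.788%), same formula.**

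| n per cohort | Where n comes from | Power |
|---|---|---|
| 265 | Table 5 footnote | 13.9% |
| 295 | 364 × 0.81, live births | 16.1% |
| 328 | 364 × 0.9, women in the analysis population | 18.6% |
| 364 | enrolled | 21.3% |
| 366 | – | 21.4% |

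Other methods at n = 265 do not give 21.4% either: pooled normal 24.3%, continuity-corrected normal 13.6%, one-sided Walters 22.1%. The printed value fits the enrolled number, not the footnoted one.

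**5. Table 5, other outcomes.** At 265, 295 or 328 per cohort and a relative risk of 3, spontaneous abortion, elective termination, preterm birth, small for gestational age (SGA) and postnatal growth deficiency all have power of at least 99.9%.

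**6. Why 295 or 328 is not a general replacement.** Table 6 narrows several denominators further. Postnatal growth deficiency excludes infants with MCM, preterm birth or SGA. Assuming independence at the reference rates, 364 × 0.81 × 0.97 × 0.9153 × 0.90 ≈ 236, before removing multiples and missing measurements. That is below 265, though Table 4 needs only 70 for a relative risk of 3.

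**The case against.** The strongest reply is that nothing is lost. The exposed targets are correct, and section 9.9 names the limited exposed population as a key limitation. Comparators at 200 and 364 exceed what is needed, so the promised precision and detectable risk are still met. Equal cohorts are a stated planning assumption, and the slack may be useful: the power calculation makes no allowance for variance added by the inverse probability weighting in 9.7.3, and the secondary comparator in 9.2 is a subset of this cohort. All of that stands, and it is a good reason to keep equal enrolment. It does not rescue the derivation. The equal-numbers assumption concerns analysable live births, which 265 against 265 already satisfies, and 9.5.2 presents 364 comparators as a requirement, not as a choice for symmetry.

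A reader might go further and infer that enrolment targets are also wrong for the other outcomes, or that Table 5's conclusions fail. The documents do not support either. Only MCM is converted to enrolment, on the stated ground that it has the most restrictive denominators, so no enrolment target for another outcome exists to be wrong. The 265 in Table 5 is openly labelled as an assumption, and every entry above 80% survives at any of the candidate sizes.

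**Conclusion.** The point holds in a limited form. The comparator minimums of 200 and 364 contain a loss that cannot occur in that cohort; the protocol's own inputs give 180 and 328, with totals of 380 and 692. The overstatement is about 11%, in the safe direction. It costs up to 36 unnecessary comparators if the figures are taken as true minimums, and no power or precision.

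In Table 5 one number is inconsistent with its footnote: stillbirth power is 13.9% at 265 by the stated method, not 21.4%. Stillbirth remains far underpowered either way, so the conclusion is unchanged.

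These results rest on the protocol's three 0.9 factors and reference rates, and on the Walters formula that reproduces Table 4. The effects of enrolment before 20 weeks, multiple gestations and missing infant data are not quantified, because the protocol gives no figures for them.

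**What to change.** 1. In 9.5.2, say that the first-trimester factor applies to the exposed cohort's MCM denominator only. Then do one of the following:
   - restate the comparator minimums as 180 and 328 (totals 380 and 692), and align the study-size statement in the abstract; or
   - keep 200 and 364 per cohort, state that equal enrolment is a choice, and report its yield: about 162 and 295 comparator live births, MCM half-width about 2.8% in that cohort, and MCM power about 82% at a relative risk of 3.
2. In Table 5 and the accompanying text, recompute the stillbirth entry and state the n used: 13.9% at 265, 16.1% at about 295, or 18.6% at about 328.
3. In the Table 5 footnote, say that 265 is the MCM count after first-trimester attrition. Do not substitute 295 or 328 for every outcome; where an outcome-specific n is given, take it from that outcome's Table 6 denominator.

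The cost is recalculation and text only, with no extra participants. The second option under item 1 leaves the recruitment plan untouched.

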9.6. Data management

9.6.1. Data collection forms

As used in this protocol, the term data collection form should be understood to refer to either a paper form or an electronic data record or both, depending on the data collection method used in this study.

A completed data collection form is required for each included patient. The completed original data collection forms are the sole property of Pfizer and should not be made available in any form to third parties, except for authorized representatives of Pfizer or appropriate regulatory authorities, without written permission from Pfizer. PPD shall ensure that the data collection forms are securely stored in SharePoint folders in encrypted electronic form and will be password protected to prevent access by unauthorized third parties. Paper forms are destroyed/shredded immediately after database entry.

PPD has ultimate responsibility for the collection and reporting of all data entered on the data collection forms and any other data collection forms as required and ensuring that they are accurate, authentic/original, attributable, complete, consistent, legible, timely (contemporaneous), enduring, and available when required. The data collection form serves as the source document. Any corrections to entries made in the data collection forms must be dated, initialed, and explained (if necessary) and should not obscure the original entry.

9.6.2. Record retention

To enable evaluations and/or inspections/audits from regulatory authorities or Pfizer, PPD agrees to keep all study-related records. The records should be retained by PPD according to

local regulations or as specified in the vendor contract, whichever is longer. PPD must ensure that the records continue to be stored securely for so long as they are retained.

If PPD becomes unable for any reason to continue to retain study records for the required period, Pfizer should be prospectively notified. The study records must be transferred to a designee acceptable to Pfizer.

Study records must be kept for a minimum of 15 years after completion or discontinuation of the study, unless PPD and Pfizer have expressly agreed to a different period of retention via a separate written agreement. Records must be retained for longer than 15 years if required by applicable local regulations.

PPD must obtain Pfizer's written permission before disposing of any records, even if retention requirements have been met.

